##### **Pharmacogenetic Biomarker Assessments**

Archived, fixed tumor tissue from the most recent surgery or biopsy will be collected (if available) from all enrolled subjects for potential assessment of mutations and other genetic alterations or genes and/or proteins that may be important in the development and progression of cancer as well as in response to study drug treatment for potential use in diagnostic development. Appropriate technology/methodologies will be used based on the amount of tumor tissue available. Note that in order to understand tumor-specific mutations, it may be necessary to compare the tumor genome with the germline genome.

A blood sample will be collected for potential genetic analysis from all enrolled subjects to evaluate whether genetic variation within a clinical study population correlates with response to the study treatment. Furthermore, it is important to evaluate germline DNA variation across the genome in order to interpret tumor-specific DNA mutations.

A blood plasma sample to isolate circulating cell-free nucleic acids will be collected at the following time points:

Treatment Period 1: Before dosing (predose) lenvatinib on Cycle 1 Day 1, Cycle 1 Day 15, Day 1 of all subsequent cycles, and at the off-treatment assessment.

Treatment Period 2: Subjects entering the subsequent TPC period should have TPC baseline sample collected unless the lenvatinib Off-Treatment visit in the lenvatinib treatment period is  $\leq 28$  days before the subsequent treatment starts, in which case those samples may be used as the TPC period baseline. Samples will then be collected at week 8 and week 16 ( $\pm 1$  week).

A detailed biomarker analysis plan will be prepared separately.

Data obtained will be used for research, to assist in developing safer and more effective treatments and will not be used to change the diagnosis of the subject or alter the therapy of the subject. The DNA will not be used to determine or predict risks for diseases that an individual subject does not currently have. Any sample or derivatives (DNA, RNA, and protein) may be stored for up to 15 years to assist in any research scientific questions related to study treatment, cancer and/or for potential diagnostic development.

Instructions for the processing, storage, and shipping of samples will be provided in the Laboratory Manual.

Biomarker correlative analyses may be performed to explore blood or tumor biomarkers that may be useful to predict subject's response in a retrospective manner. The results of these studies are to gain further insight into the clinical mechanism of action for study drug but not foreseen to result in commercially valuable products.

This study will collect biomarker samples in all enrolled subjects who have consented for participation of the biomarker assessments. Participation of any future exploratory research of leftover material will be optional.

#### 9.5.1.5 Safety Assessments

Safety assessments consisted of monitoring and recording of all AEs, including all CTCAE v4.03 grades (for increasing severity), and serious adverse events (SAEs); regular laboratory evaluation for hematology, blood chemistry, and urine dipstick values; periodic measurement of ECOG PS, Child-Pugh score, vital signs, 12-lead electrocardiograms (ECGs), and echocardiograms or MUGA scans including LVEF; and the performance of physical examinations as detailed in [Table 3](#).

Safety assessments will be performed at intervals as indicated in Schedule of Procedures/Assessments ([Table 3](#)) in both Treatment Periods. .

##### 9.5.1.5.1 ADVERSE EVENTS

An AE is any untoward medical occurrence in a patient or clinical investigation subject administered an investigational product. An AE does not necessarily have a causal relationship with the medicinal product.

The criteria for identifying AEs in this study are:

- Any unfavorable and unintended sign (including an abnormal laboratory finding), symptom, or disease temporally associated with the use of an investigational product, whether or not considered related to the investigational product (Note: Every sign or symptom should not be listed as a separate AE if the applicable disease [diagnosis] is being reported as an AE).
- Any new disease or exacerbation of an existing disease. However, worsening of the primary disease (HCC) should be captured under efficacy assessments as disease progression rather than as an AE. If the disease progression leads to an untoward medical occurrence, then this medical occurrence should be recorded as an AE.

- Any deterioration in nonprotocol-required measurements of a laboratory value or other clinical test (eg, ECG or x-ray) that results in symptoms, a change in treatment, or discontinuation of study drug.
- Recurrence of an intermittent medical condition (eg, headache) not present pretreatment (Baseline).
- An abnormal laboratory test result should be considered an AE if the identified laboratory abnormality leads to any type of intervention, withdrawal of study drug, or withholding of study drug, whether prescribed in the protocol or not.

All AEs observed during the study will be reported on the CRF. All AEs, regardless of relationship to study drug or procedure, should be recorded beginning from the time the subject signs the study ICF through the last visit and for 28 days after the last dose of lenvatinib treatment if subjects do not enter TPC period, or for 8 weeks after the start of TPC period. SAE information should be collected for 8 weeks after the start of the TPC, or for at least 28 days after the last dose of lenvatinib/TPC if subjects do not continue into the TPC period or do not stay in the TPC period for the 8 weeks of safety monitoring.

Abnormal laboratory values should not be listed as separate AEs if they are considered to be part of the clinical syndrome that is being reported as an AE. It is the responsibility of the investigator to review all laboratory findings in all subjects and determine if they constitute an AE. Medical and scientific judgment should be exercised in deciding whether an isolated laboratory abnormality should be classified as an AE. Any laboratory abnormality considered to constitute an AE should be reported on the Adverse Event CRF.

Abnormal ECG (QTc) results, if not otherwise considered part of a clinical symptom that is being reported as an AE, should be considered an AE if the QTcF interval is more than 450 ms and there is an increase of more than 60 ms from baseline. Any ECG abnormality that the investigator considers as an AE should be reported as such.

**Every effort must be made by the investigator to categorize each AE according to its severity and its relationship to the study treatment.**

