#### 9.1.2.2 Subsequent Treatment Period (TPC Period, Treatment Period 2)

The subsequent TPC period will begin upon the completion of the lenvatinib Off-Treatment Visit in first-line treatment of lenvatinib. Subjects will be treated with commercially available systemic TPC for uHCC. The first treatment of a single agent or combination of multiple drugs after lenvatinib treatment will be considered as the subsequent TPC. Locoregional therapies (ie, chemoembolization/radioembolization, etc) procedures will not

be considered as a second line treatment following lenvatinib. If the investigator deems a subject inappropriate for commercially available systemic TPC as the subsequent treatment following lenvatinib, subjects will be followed in the survival Follow-Up period. All treatment following lenvatinib will be captured in the case report form. Data will be collected from the start of TPC, then at intervals as indicated in Schedule of Procedures/Assessments ([Table 3](#)).

Subjects starting subsequent TPC  $\geq$ 8 weeks after lenvatinib off-treatment visit may be considered after discussion with sponsor.

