#### 9.5.1.6 Other Assessments

Subjects perceived burden post lenvatinib treatment in the subsequent TPC period will be measured by completed PRO-CTCAE questionnaires. PRO-CTCAE data will be collected only at the lenvatinib Off-Treatment Visit in Treatment Period 1, and every 2 weeks for the first 4 weeks, and then at week 8 and week 16 ( $\pm 1$  week) in the TPC period. A TPC baseline assessment should be performed unless the lenvatinib Off-Treatment visit is completed within 7 days prior to the first TPC treatment.

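### On TPC, adverse events and serious adverse events have differently worded start dates, and only serious events have a 28-day early-stop clause; both need one rule from first TPC dose

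*Combined protocol and SAP*

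**What the plan says.** **AEs.** Section 9.5.1.5.1 records all AEs "beginning from the time the subject signs the study ICF through the last visit and for 28 days after the last dose". The dose meant there is the last one of lenvatinib, and this limit applies "if subjects do not enter TPC period, or for 8 weeks after the start of TPC period". Table 3 footnote z repeats the 28-day and 8-week parts but leaves out the reference to a last visit. The Table 3 row for AEs/SAEs says only that they are collected throughout.

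**Start of the period.** Section 9.1.2.2 states: "The subsequent TPC period will begin upon the completion of the lenvatinib Off-Treatment Visit in first-line treatment of lenvatinib". The synopsis and Section 9.4.1.2 agree.

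**SAEs.** The next sentence of 9.5.1.5.1 reads "SAE information should be collected for 8 weeks after the start of the TPC". It then gives a minimum for those who never go on to TPC: "or for at least 28 days after the last dose of lenvatinib/TPC if subjects do not continue into the TPC period". The same 28-day minimum is also extended to subjects who leave TPC before the 8 weeks of monitoring are over. Section 9.5.4.1 and footnote z carry the same SAE rule.

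**Concomitant medications.** Sections 9.4.7 and 9.7.1.5 and footnote y use the period start, as the AE rule does. They add a clause of up to 28 days after the last TPC dose for early stoppers.

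**The gap before TPC.** The protocol expects that the Off-Treatment Visit and first TPC dose may be apart. For PRO-CTCAE, Section 9.5.1.6 says: "A TPC baseline assessment should be performed unless the lenvatinib Off-Treatment visit is completed within 7 days prior to the first TPC treatment". Footnote s uses 28 days for biomarker samples. Section 9.1.2.2 adds that starts at 8 or more "weeks after lenvatinib off-treatment visit may be considered after discussion with sponsor".

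**Use in the analysis.** Section 9.7.1.1.1 bases the primary endpoint on TEAEs and SAEs. Section 9.7.1.8.2 defines TEAEs separately for each treatment period, as events emerging or worsening during treatment, and gives no window in days.

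**The concern.** An incidence proportion can be interpreted only if the observation window is known and is the same for all subjects. Two features of the wording work against that.

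First, the AE clock uses a term that the protocol ties to the Off-Treatment Visit, while the SAE clock uses the start of treatment. A site that applies the defined term closes its AE window early on TPC, by the length of the gap. A site that counts from first dose does not. With 20 to 25 sites, both readings could occur, and Period 2 AE incidence would then mix windows of different length.

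Second, a subject who stops TPC before Week 8 has an SAE minimum that moves with the last dose, while the AE end date does not. Serious and non-serious events in the same subject can therefore be followed for different times after TPC.

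**Working it through.** **Inputs.** 8-week AE and SAE windows and the 28-day SAE minimum (9.5.1.5.1, 9.5.4.1, footnote z); gap thresholds of 7 days (9.5.1.6), 28 days (footnote s) and 8 weeks (9.1.2.2); n = 100, 50% to 100% receiving TPC, and a 75% Grade 3 or higher TEAE rate (9.7.2).

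**1. The plan's own figure.** Half width = 1.96 × √(0.75 × 0.25 / n). For n = 100, 90, 80, 70, 60 and 50 this gives 8.49, 8.95, 9.49, 10.14, 10.96 and 12.00%. Table 4 states 8.5, 8.9, 9.5, 10.1, 11 and 12% (the second value is 8.946 before rounding). All six rows reproduce. The formula uses only n and the rate, so the collection window does not enter it.

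**2. Start date.** Let g be the weeks from the Off-Treatment Visit to first TPC dose. Taking the 8-week clause alone and literally, AE weeks recorded on TPC = max(0, 8 − g). Counting from first dose, the answer is 8 for every g.

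| Gap | AE weeks on TPC, literal | Loss |
|---|---|---|
| 0 | 8 | 0 |
| 7 days (g = 1) | 8 − 1 = 7 | 1/8 = 12.5% |
| 28 days (g = 4) | 8 − 4 = 4 | 4/8 = 50% |
| 8 weeks (g = 8) | 8 − 8 = 0 | 100% |

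The 7- and 28-day rows are thresholds for reusing a baseline, not expected delays. The last row needs prior discussion with the sponsor. The loss column is an upper bound.

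**3. End date.** The undefined last visit adds a third reading. If it meant the Week 16 visit, AEs would run to Week 16. A 28-day gap then gives 4, 8 or 16 weeks of AE recording on TPC, depending on the reading. Footnote aa limits collection after Week 16 to tumor assessments and TPC dosing. It does not name AEs and does not settle the matter.

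**4. Early stop, with both windows counted from first TPC dose.** For a stop at week s < 8, the AE end is Week 8 and the SAE minimum ends at s + 4, so the difference is s − 4. AE days after the last dose = 7 × (8 − s).

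| Stop (s) | AE end | SAE minimum end | SAE − AE | AE days after last dose | max(8, s + 4) |
|---|---|---|---|---|---|
| 1 | 8 | 5 | −3 | 49 | 8 |
| 2 | 8 | 6 | −2 | 42 | 8 |
| 4 | 8 | 8 | 0 | 28 | 8 |
| 5 | 8 | 9 | +1 | 21 | 9 |
| 6 | 8 | 10 | +2 | 14 | 10 |
| 7 | 8 | 11 | +3 | 7 | 11 |

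Just before Week 8 the difference approaches +4 weeks. AE follow-up is the shorter of the two only for stops between Weeks 4 and 8. Since s < 8, the AE window still covers all time up to the last dose, so the shortfall lies wholly after it. The last column is the end date under a single rule. It is never below 8 or below s + 4.

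**The case against.** The strongest reply is that first TPC dose was plainly meant. Section 9.1.2.2 says "Data will be collected from the start of TPC, then at intervals as indicated in Schedule of Procedures/Assessments"; the safety visits fall at TPC Weeks 2, 4 and 8; and the SAE sentence itself uses treatment and period loosely. That stands as the likely intent. It is also argued that the literal reading defeats itself, because everyone who completes the Off-Treatment Visit would then have entered the period, leaving nobody for the no-entry clause. That does not stand. Subjects judged inappropriate for TPC go from that visit to survival follow-up (9.1.2.2, 9.1.2.3), so the clause keeps a meaning under the literal reading.

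It is also fair that the missing early-stop clause may hardly touch the primary incidence. Section 9.7.1.8.2 counts events during treatment and states no post-dose lag, and the affected time is all after the last dose.

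A reader might go further and infer that the primary endpoint and the 75% planning rate should be restated as 8-week incidences, with later events excluded. The documents do not support that. Section 9.7.2 gives the 75% no time basis. Counting to Week 8 regardless of stopping would conflict with the during-treatment definition, and the added AE tail would then never reach the endpoint.

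Finally, a site may not know 28 days after lenvatinib whether TPC will start. That is true, but the present rule branches on the same question.

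**Conclusion.** The point holds as a wording defect in the collection rules behind the primary endpoint. Two things are established from the text: the AE and SAE clocks are worded to start at different events, and AEs lack the early-stop clause that SAEs and concomitant medications have.

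The size is unknown. For the start date, the loss of non-serious AE recording on TPC equals the gap, up to the full 8 weeks, and is zero at sites that count from first dose. That range assumes the 8-week clause is read alone. For early stoppers, with first dose as common start, the AE shortfall against the SAE minimum is between 0 and just under 4 weeks. It applies only to stops between Weeks 4 and 8 and falls only after the last dose.

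Two stronger inferences should be resisted. One is that AE follow-up is always the shorter: for stops up to Week 4 it equals or exceeds the SAE minimum. The other is that a known share of events will be missed: with no gap distribution and no time basis for the 75%, lost weeks cannot be converted into lost incidence. The sample-size table is correct as it stands.

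**What to change.** In 9.5.1.5.1, 9.5.4.1 and Table 3 footnote z, state one rule for AEs and SAEs:

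- If TPC is started, record through 8 weeks after the date of first TPC dose. If TPC stops before 8 weeks, record through the later of that date and 28 days after the last TPC dose.
- If TPC is not started, record through 28 days after the last lenvatinib dose.

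Use the same first-dose start for concomitant medications (9.4.7, 9.7.1.5, footnote y). Define the last visit in 9.5.1.5.1 or delete the reference. Have the per-period TEAE definition in 9.7.1.8.2 refer to this common window for both TEAEs and SAEs, with matching SAP text. Leave the primary endpoint and the 75% planning rate as they are.

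The cost is an amendment to wording and some extra entries: SAEs for up to 3 more weeks after a Week 1 stop (8 − 5), AEs for up to about 4 more weeks for stops between Weeks 4 and 8, and AEs during any gap before TPC. Some of these entries fall after the Week 8 visit, and Table 3 schedules no further visit until Week 16. No procedure is added. Neither the 8-week AE clause nor the 28-day SAE minimum is shortened, and Table 4 does not change.

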### **Assessing Severity of Adverse Events**

Adverse events will be graded on a 5-point scale according to CTCAE v4.03. Investigators will report CTCAE grades for all AEs (for increasing severity).

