- n: Clinical laboratory tests (hematology and clinical chemistry) will be performed at local laboratory. Laboratory tests at Baseline may be performed up to 72 hours prior to first dose of lenvatinib treatment. Review hematology clinical chemistry results within 48 hours after receiving quick estimation. Assessments scheduled may be performed within 72 hours prior to the visit. If  $\geq$  Grade 3 hematologic or clinical chemistry toxicities, repeat laboratory test and AE assessment at least every 7 days (until improvement to  $<$ Grade 3). Clinical laboratory tests will be performed at week 2, week 4, and week 8 ( $\pm 1$  week) in TPC period. A TPC baseline assessment should be performed unless the lenvatinib Off-Treatment visit is completed  $\leq 7$  days prior to the first TPC treatment.
- o: For subjects with proteinuria  $\geq 2+$  (see the dose adjustment table for management of proteinuria).
- p: A serum or urine pregnancy test will be performed in women of childbearing potential (ie, premenopausal women and postmenopausal women who have been amenorrheic for less than 12 months). A separate baseline assessment is required if a negative screening pregnancy test was obtained more than 72 hours before the first dose of study drug.
- q: PRO-CTCAE data will be collected at the following time points: lenvatinib Off-Treatment Visit during Treatment Period 1, every 2 weeks for the first 4 weeks, and then at week 8 and week 16 ( $\pm 1$  week) in Treatment Period 2. A TPC baseline assessment should be performed unless the lenvatinib Off-Treatment visit is completed  $\leq 7$  days prior to the first TPC treatment.
- r:  $\alpha$ -Fetoprotein (AFP) and thyroid-stimulation hormone (TSH) will be measured at screening visit, Baseline, on C1D15, C2D1, C3D1, and every 2 cycles thereafter (C5D1, C7D1, C9D1, etc) in Treatment Period 1, and week 8 and week 16 ( $\pm 1$  week) in TPC period. A TPC baseline assessment should be performed unless the lenvatinib Off-Treatment visit is completed  $\leq 7$  days prior to the first TPC treatment.

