#### 9.7.1.8.2 ADVERSE EVENTS

Adverse Events will be graded using CTCAE v4.03. The AE verbatim descriptions (investigator terms from the CRF) will be classified into standardized medical terminology using the Medical Dictionary for Regulatory Activities (MedDRA). Adverse events will be coded to the MedDRA lower level term (LLT) closest to the verbatim term. The linked MedDRA preferred term (PT) and primary system organ class (SOC) are also captured in the database.

A TEAE is defined as an AE that emerges during treatment, having been absent at pretreatment (baseline) or

- Reemerges during treatment, having been present at pretreatment (baseline) but stopped before treatment, or
- Worsens in severity during treatment relative to the pretreatment state, when the AE is continuous.

TEAE will be defined and summarized for each treatment period separately.

Only those AEs that are treatment emergent will be included in summary tables. All AEs, treatment emergent or otherwise, will be presented in subject data listings.

The incidence of TEAEs will be reported as the number (percentage) of subjects with TEAEs by SOC and PT. A subject will be counted only once within an SOC and PT, even if the subject experienced more than 1 TEAE within a specific SOC and PT. The number (percentage) of subjects with TEAEs will also be summarized by highest CTCAE grade. The number (percentage) of subjects with TEAEs will also be summarized by relationship to study drug (probably related, possibly related, and not related).

The number (percentage) of subjects with treatment-related TEAEs will be summarized by SOC and PT. Treatment-related TEAEs include those events considered by the investigator to be related to study treatment.

The number (percentage) of subjects with treatment-emergent SAEs will be summarized by MedDRA SOC and PT. A subject data listing of all SAEs will be provided.

The number (percentage) of subjects with TEAEs leading to discontinuation from study drug or leading to study drug dose changes will be summarized by MedDRA SOC and PT. A subject data listing of all AEs leading to discontinuation from study drug or leading to study drug dose changes will be provided.

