#### 9.7.1.8.3 LABORATORY VALUES

Laboratory results will be summarized using Système International (SI) units, as appropriate. For all quantitative parameters, the actual value and the change from baseline to each postbaseline visit will be summarized by visit using descriptive statistics. Qualitative parameters will be summarized using frequencies (number and percentage of subjects).

Percentages will be based on the number of subjects with both nonmissing baseline and at least 1 postbaseline results.

Laboratory parameters will be categorized according to CTCAE v4.03 grades, and shift tables from baseline CTCAE grades to the maximum/worst and final postbaseline grades will be provided.

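### The protocol does not ask for the grade of ongoing AEs at TPC start, so some carried-over lenvatinib AEs may be misclassified in the primary TPC-period TEAE summary

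*Combined protocol and SAP*

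**What the plan says.** **Collection.** Section 9.5.1.5 describes AE monitoring as "including all CTCAE v4.03 grades (for increasing severity", and the severity paragraph of Section 9.5.1.5.1 repeats it: "Investigators will report CTCAE grades for all AEs (for increasing severity". Section 9.5.1.5.1 also says "All AEs observed during the study will be reported on the CRF".

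**Classification.** Section 9.7.1.8.2 states "TEAE will be defined and summarized for each treatment period separately". Besides AEs absent before treatment, it counts an AE that "Reemerges during treatment, having been present at pretreatment (baseline) but stopped before treatment, or" one that "Worsens in severity during treatment relative to the pretreatment state, when the AE is continuous".

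**TPC Baseline.** The footnotes to Table 3 give a TPC-baseline rule for ECOG PS, Child-Pugh score, vital signs, urine dipstick, physical examination, ECG, laboratory tests, PRO-CTCAE, special chemistries, biomarkers and tumor imaging. Most use the form "A TPC baseline assessment should be performed unless the lenvatinib Off-Treatment visit is completed" within 7 days before the first TPC treatment. The AE/SAE row is marked as running throughout the study, and its footnote z has no TPC-baseline rule.

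**Sample size.** Section 9.7.2 justifies 100 subjects by the precision of the Grade 3 or higher TEAE rate among TPC recipients, assumed to be 75%.

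**The concern.** To decide whether a continuous AE worsened on TPC, the analyst needs its grade just before TPC. The collection rule is worded for rises in grade. It does not ask for a fall, and no visit asks for the current grade of AEs still open when TPC begins.

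Easing without resolution is an expected course. Table 1 has lenvatinib interrupted for non-hematologic toxicity until the event reaches Grade 0-1 or baseline, so an event may settle at Grade 1 and stay open. Unacceptable toxicity is also a listed reason to stop lenvatinib.

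The protocol does not define the pretreatment state for TPC-period TEAEs either. A SAP can supply that definition later, but it cannot recover a grade that was never collected. What is at stake is the classification of carried-over events in the primary summary, and so the Grade 3 or higher rate on which the sample size rests.

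**Working it through.** **1. The plan's own figure.** Inputs from Section 9.7.2: N = 100, p = 0.75, TPC share 50% to 100%. Half-width = 1.96 × √(p(1 − p)/n).

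| n on TPC | Computed (points) | Table 4 |
|---|---|---|
| 100 | 8.487 | 8.5% |
| 90 | 8.946 | 8.9% |
| 80 | 9.489 | 9.5% |
| 70 | 10.144 | 10.1% |
| 60 | 10.957 | 11% |
| 50 | 12.002 | 12% |

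Table 4 reproduces. The planning measure is the proportion of TPC recipients with at least one Grade 3 or higher TEAE.

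**2. How the choice of reference changes the classification.** Each row is a non-laboratory AE that began on lenvatinib: peak grade on lenvatinib → grade at TPC start → worst grade on TPC. Each cell gives its TPC-period status. The last column assumes the AE was absent at study Baseline.

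| Course | Last grade before TPC as reference | Highest lenvatinib-period grade as reference | Study Baseline as reference |
|---|---|---|---|
| 3 → 1 → 3 | TEAE, Grade 3 | not a TEAE | TEAE, Grade 3 |
| 3 → 1 → 2 | TEAE, Grade 2 | not a TEAE | TEAE; Grade 3 if the form carries the event's highest grade |
| 3 → 1 → 1 | not a TEAE | not a TEAE | TEAE; Grade 3 if the highest grade is carried |
| 3 → 0 → 3 | TEAE (re-emerged) | TEAE (re-emerged) | TEAE |
| 3 → 1 → 4 | TEAE, Grade 4 | TEAE, Grade 4 | TEAE, Grade 4 |

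The first column follows the natural reading of Section 9.7.1.8.2, but it needs the middle grade, which the collection rule does not ask for. If the form keeps only rises or the worst grade, the analyst is left with the second or third column. The second under-counts rows 1 and 2. The third can overstate rows 2 and 3. Rows 4 and 5 are safe under any reference.

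**3. Size per subject.** One subject out of n moves the rate by 1/n: 1/50 = 2 points at 50 recipients and 1/100 = 1 point at 100. This is an upper limit, because a subject with another Grade 3 or higher TPC TEAE is counted anyway.

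**4. Why no total can be given.** Assume, with no support in the documents, that 10% to 30% of TPC recipients start with an eased, unresolved Grade 3 or higher AE, that one third of these worsen again to that level, and that all are missed. The affected share is x = 0.10/3 = 3.3% to 0.30/3 = 10%.

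- If none of them has another Grade 3 or higher TEAE, the loss is x, or 3.3 to 10 points.
- If other Grade 3 or higher TEAEs occur independently and the true total is 75%, the share with no other such TEAE is 0.25/(1 − x). The loss is x × 0.25/(1 − x): 0.0333 × 0.2586 = 0.9 points, to 0.10 × 0.2778 = 2.8 points.

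For the same assumed share of affected subjects, the answer runs from about 1 point to 10.

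**The case against.** The strongest reply is that the text is not as restrictive as it may look. A reader might infer that grades are recorded only when they rise, that the grade at TPC start is never captured, and that a re-worsening AE cannot be counted. The documents support none of these.

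- The grading rule does not say only, and no section forbids entering a lower grade.
- A move from Grade 1 to Grade 3 on TPC is itself a rise in severity, so the rule asks for it. Section 9.5.1.5.1 also lists exacerbation of an existing condition among its AE criteria, and AEs are collected for 8 weeks after TPC start.
- The definition is sound on its natural reading: for TPC, the pretreatment state is the state before TPC. The weakness is in data capture.
- Laboratory, vital-sign, ECG and dipstick findings have a value at TPC Baseline, or from an Off-Treatment Visit no more than 7 days earlier. Section 9.7.1.8.3 adds "Laboratory parameters will be categorized according to CTCAE v4.03 grades, and shift tables from baseline CTCAE grades".
- AEs that stopped and returned, AEs that exceed their lenvatinib peak, and AEs still at their last recorded grade are handled correctly.
- The CRF, its Completion Guidelines and the separate SAP are not in the documents, and they may already settle how grade changes are entered.

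All of this stands, and it narrows the point to clinically graded AEs that ease, persist, and worsen again to no more than their earlier peak. It does not remove it. A reported rise still needs a recorded lower grade to be compared with, and the protocol does not require one. An AE row that runs throughout the study shows that AEs are followed, not that the current grade is entered when TPC starts.

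**Conclusion.** The point holds in this limited form. The protocol does not require a fall in grade, or the grade of ongoing AEs at TPC start, to be recorded, and it does not define the AE baseline for the TPC period. A specific class of carried-over, non-laboratory AEs may therefore be misclassified in the primary summary.

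The effect is up to 2 points in the Grade 3 or higher rate per misclassified subject at 50 TPC recipients. It reaches that limit only if the subject has no other such TEAE on TPC.

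A reader might go further and infer that TPC will necessarily look safer than it is, or that the bias is some 3 to 10 points. Neither is supported. The direction depends on the reference used: the highest lenvatinib-period grade under-counts, and the study Baseline can over-count. The documents do not say how often lenvatinib AEs ease without resolving or worsen again on TPC, so the total bias is unknown. The conclusion also rests on the protocol alone; a CRF that dates every grade change would close most of the gap.

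**What to change.** 1. At TPC Baseline, or at the lenvatinib Off-Treatment Visit when it serves as TPC baseline, record the current CTCAE grade of every ongoing AE. Add this to footnote z of Table 3 and to the severity paragraph of Section 9.5.1.5.1.
2. During the TPC period, record any later rise above that grade as a dated severity entry.
3. In Section 9.7.1.8.2, state that the pretreatment state for TPC-period TEAEs is the last grade before the first TPC dose, and carry the same sentence into the SAP.

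The cost is one extra CRF field per ongoing AE at an existing visit, some added data entry for later rises, and a few lines of text. No new visit or procedure is needed. If the CRF Completion Guidelines already require dated entries for every grade change, including falls, only step 3 remains.
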